Missing data values will be minimized by intensive training of the assessors in techniques of clarifying answers and checking questionnaires while participants are on-site. When missing values are identified, several approaches to acquire the necessary data will be employed: 1) if at all possible, participants will be rescheduled within 24 hours of completion of tests or interviews; 2) if a participant cannot be rescheduled, an effort will be made to send a tester to the individual's place of residence within the same period; 3) missing data will be examined to assess randomness. We expect missing data to be randomly distributed and will impute appropriate values (see below). Missing data (i.e., loss to follow up) will be tested to determine if it is informative, and the methods developed by [82] and [83] to test for completely random dropouts will be applied. If necessary, the techniques of [84] applicable to generalized

estimating equations models will be used to impute missing values.

We will test whether drop-out is random or systematic by comparing the drop-outs with the study completers on the baseline data. An absence of significant differences would support the random nature of drop-outs. Effect of drop-outs will be minimized by the following steps: First, selected data analysis method allows the inclusion of subjects who drop-out or were terminated early in the study, without relying on data imputation procedures. Therefore, no subjects will be excluded from the analyses due to their study status. Second, effect of any systematic differences between the drop-outs and completers will be explored by including the variable of concern to the model as a covariate.

9.11.2. Primary Outcome Analyses.

Hypothesis 1: Veterans in TrIGR, compared to Veterans in SCT, will have significantly greater reductions in deployment-related guilt severity (TRGI) at the end of treatment and follow-up period. This hypothesis will be tested using Mixed Effects models. We will examine two specific forms of the Mixed effects model strategy; random regression models (RRM), also known as hierarchical models (HLM), Linear Mixed Effects models (LMEs) or multilevel models; and mixed model analysis of variance (MMANOVA). The Hierarchical Linear Model assumes that change over time is linear while MMANOVA considers time as a categorical classification variable and does not assume any specific profile between the outcome variable and time. Each outcome variable will be graphed versus time for each subject to evaluate what function of time bests describes the data. If the change is linear we will precede with the LMEs structure. If the time pattern is not immediately apparent we will proceed with the MMANOVA. This method allows the inclusion of subjects with missing data or those who were terminated early in the study, without relying on data imputation procedures. A fully saturated treatment by time model will be utilized for inference. Co-variance structure will be chosen based on Akaike's Information Criterion (AIC). Random group level treatment effects will also be evaluated for importance based on the model AIC. Denominator degrees of freedom will be calculated using the Kenward-Roger small sample correction.

Data will be analyzed from all randomized subjects on whom we have a baseline assessment and at least one post-baseline evaluation. Responses at baseline through 6 months follow-up will be nested within subjects. Slope (change in outcome over time) will be entered into the model as a random factor and interacted with treatment group. Intercept and slope will be modeled as random effects nested within subject, and treatment group will be a fixed effect. If it is needed based on analyses in stage one, baseline covariates (e.g., demographics) will also be entered as fixed effects. Site and the Treatment by Site interaction will be included as “nuisance parameters;” that is, they must be included to account for possible overall site effects (Site) or possible site differences in treatment effects (Treatments X Site). With the balanced design (equal numbers at each site in each group), ignoring these would not increase the probability of Type I error, but it would increase the Error Sum of Squares, thus increasing the probability of Type II Error. The main effect of treatment represents the common effect size across sites if there is one, or the average site effect, if there is heterogeneity across sites. This is true because sample sizes will be balanced across treatment groups and sites. In any case, the analysis procedures will include site and site interaction effects to avoid allowing site effects to bias treatment comparisons. However, if we detect any imbalances between the treatment groups within each site, we will follow the primary analyses above with subsequent analyses considering the imbalances to verify that the conclusions are not affected by the imbalances.

Hypothesis 2: Veterans in TrIGR, compared to Veterans in SCT, will have significantly greater reduction in distress (BSI-18), shame (ISS), and significantly more improved in their quality of life (WHO-QOL-BREF) at the end of treatment and at follow up periods. This hypothesis will be analyzed using a method similar to that for testing hypothesis 1.

Hypothesis 3: Per the NAG model, guilt cognitions (TRGI Cognitions Scale), distress (BSI-18) and avoidant coping (COPE) will partially mediate the treatment effect on guilt severity (TRGI). For this hypothesis, we will use the same mixed effect model procedure identified in hypothesis 1. We will utilize the analytic strategy described by [85] [86] to test the mediation effect. Based on this strategy, four conditions must be met: (1) a significant relationship between the independent variable (i.e., intervention

condition) and the dependent variable, (2) a significant relationship between the independent variable and the proposed mediator, (3) a significant relationship between the mediator and the outcome, and (4) the relationship between the independent variable (intervention) and outcome must be significantly lower after controlling for the proposed mediator. To test for significant mediation, we will conduct a Sobel test. We will also use the formula provided by [87] to determine the percentage of the intervention condition to primary outcome path that was accounted for by change in our mediator [88].

Exploratory Analyses. The first exploratory objective, whether TrIGR, as compared to SCT, is associated with greater decreases in PTSD and depression symptom severity, greater reductions in suicidal ideation (SI) and greater reductions in alcohol/substance use, will be explored using mixed effect method as explained for hypothesis 1. The second and third objectives—whether reductions in guilt, shame, and avoidant coping will partially mediate the treatment effect on PTSD symptoms among Veterans with a PTSD diagnosis and among Veterans with a depressive disorder—will be explore using analytic strategy as described for hypothesis 3 [85].

Power analysis. Overall, assumptions for our sample size estimation were: (1) sufficient power to test different hypotheses using different analytical models; (2) the reality of recruiting subjects and conducting the study; (3) project cost considerations; and (4) study duration. Therefore, for hypotheses 1 and 2, we performed our calculations using several different methods, each with varying levels of complexity and selected a sample size that provided us with a minimum of 80% power for medium to large effect sizes in each case. The medium effect size was chosen based on the findings reported above. First, we estimated the power using an analysis of variance (ANOVA) in which the person-specific regression coefficient can be used as the dependent variable. Second, we used the method provided by Hedeker and colleagues for the Random Regression Model [80] and finally, we used the RMASS program provided by Hedeker (<http://tigger.uic.edu/~hedeker/ml.html>). Overall, we believe that the proposed sample size of 150 subjects would provide us with minimum of 90% power to detect the medium effect size for hypothesis 1 and 80% for hypothesis 2. Note: Medium effect size is defined as a between-group difference increasing linearly from 0 at baseline to .5 SD units at the last time point. The minimum power estimation is based on sample size calculation for 10% to 20% attrition, correlations of 0.2, 0.5, and 0.8 between the repeated measures, and for medium and large effect sizes. For hypothesis 3, we used the procedures defined by [89] for estimating sample sizes needed to achieve 80% power to detect the mediated effect. They defined regression coefficients of .14, .39, and .59 to be small, medium, and large, respectively. For mediation analysis, we also assume a medium effect based on finding reported above. Using the Sobel test procedure, we estimated that with the proposed sample we will achieve 80% power to detect a mediated effect.

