Trauma Informed Guilt Reduction Therapy

NCT02512445

Original Document Date: November 14, 2024

8. Aims and Objectives

Primary Aim: To evaluate the efficacy of TrIGR for reducing deployment-related guilt in Veterans of OEF/OIF/OND.

Hypothesis 1: Veterans in TrIGR compared to Veterans in supportive care therapy (SCT), will have significantly greater reductions in deployment-related guilt severity at the end of treatment and post-treatment follow-up.

Secondary Aims: To examine whether TrIGR reduces distress and shame and improves quality of life. We are also interested in the degree to which gains are maintained during the follow up periods.

Hypothesis 2: Veterans in TrIGR, compared to Veterans in SCT, will have significantly greater reductions in distress, shame, guilt cognitions, avoidant coping, and significantly more improvement in their quality of life at the end of treatment and at post-treatment follow-up.

Hypothesis 3: Per the NAG model, guilt cognitions, distress and avoidant coping will partially mediate the treatment effect on guilt severity.

Exploratory Aim: By including Veterans with a variety of deployment-related presenting problems, we will be able to conduct exploratory analyses that will inform future research regarding for whom and under what conditions TrIGR is most effective.

Objective 1: To explore relationships between TrIGR effects and PTSD and depression symptom severity, suicidal ideation (SI) and alcohol/substance use.

Objective 2: To explore whether reductions in guilt, shame, and avoidant coping will partially mediate the treatment effect on PTSD symptoms among **Veterans with a PTSD diagnosis** and/or depression symptoms among **Veterans with a depressive disorder**.

9. Approach

9.1. Design. This prospective, randomized, controlled trial will assess the efficacy of TrIGR as compared to SCT for the treatment of male and female Veterans with guilt related to a traumatic event that occurred during deployment. 150 participants will be enrolled through the San Diego and Providence VAs and randomized at the individual level. All eligible participants will complete an in-person baseline assessment, receive 6 sessions of TrIGR or SCT in individual format, complete weekly measures related to the primary and secondary aims, and complete a follow-up assessment immediately post-treatment, and 3- and 6-months later.

9.2. Timeline. We propose a study lasting 4 years including:

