Phase I Set up (months 0 - 5): Start-up activities will include finalizing approvals, hiring and training of the research staff and therapists providing the study interventions, and setting up data entry and management procedures in collaboration with study statistician, [name]. Patient recruitment protocols will be developed, tested, and revised.

Phase II RCT (months 6 - 42): Participant recruitment and enrollment will occur in months 6 to 34, with the intervention period occurring from months 6 to 36. Assessment will continue for an additional six months past the end of the intervention period (to month 42) to complete the final follow-up assessments. Methods and procedures are consistent with CONSORT guidelines for conducting and reporting RCT's [49]. We expect to recruit 2-3 participants per site per month, which will allow us to meet our recruitment target of 150. Data entry and management will begin with preliminary statistical analyses in the second year and will continue through the end of the study.

Phase III Dissemination (months 43 - 48): The final six months will be used for data analysis and dissemination of results via conferences and in manuscripts.

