9.3. Procedures. Eligible Veterans will be recruited from two VA Medical Center sites, one in San Diego, CA, and one in Providence, RI. Potential participants will be receiving or presenting to care at VA enrollment, primary care, mental health, MST, or other VA services and will be referred by clinicians or staff in those clinics (see letters in Support 2e - 2g). Veterans may also self-refer to the study in response to advertising materials that will be distributed in patient areas and in the community. All potential participants will undergo a brief (15 minute) screen (following informed consent to be screened) conducted by the site project coordinator to determine preliminary eligibility. Veterans who meet the screening requirements will complete consenting procedures and will be invited for a full baseline assessment. Participants who meet inclusion/exclusion criteria as confirmed by the baseline assessment will be randomized to TrIGR or SCT. All participants will be assessed at baseline, immediately post-treatment, and at 3- and 6-month post-treatment follow-ups. Participants will be compensated for completing each of the four assessments with \$40 per assessment. We anticipate that baseline assessments will take approximately 3 hours and follow-ups will take approximately 2 hours. Participants will also complete brief weekly self-report assessments (15 minutes) during treatment. We will attempt to obtain follow-up data on all participants, regardless of whether they complete the intervention.

9.4. Participants: Inclusion/Exclusion Criteria, and Rationale. Participants will be male and female OEF/OIF/OND Veterans, at least 18 years of age, who endorse distress from guilt related to an event or events that occurred during a military deployment. Women and members of diverse ethnic and racial groups will be recruited for this project. Eligibility criteria were designed to recruit a heterogeneous and representative sample of Veterans with guilt and distress related to trauma that occurred on deployment. Eligibility criteria are broad in order to capture the many manifestations of distress related to guilt among Veterans.

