9.7.4. Treatment Fidelity. Our approach to treatment fidelity and adherence utilizes accepted standards [65] including: (1) treatment manuals with weekly objectives, outcomes, and agendas, (2) therapist training (to avoid bias, therapists will be trained for both interventions), and (3) ongoing evaluation of treatment fidelity through audio-rating of therapy sessions and supervision. To identify problems early, [name] will listen to audio-recordings of each therapist once per week for a period of 6 weeks post-training and complete fidelity rating sheets for each session (see Appendix 12f-g). Corrective feedback will be provided as needed. Thereafter, [name] (who is trained to fidelity and experienced in delivering and rating fidelity for both TrIGR and SCT) will rate 10% of remaining audio-recorded sessions at random as determined by the study statistician, [name]. Further, Drs. [name] (for TrIGR) and [name] (for SCT) will have weekly supervision of therapists to evaluate their implementation of and adherence to the therapy manuals. The participant evaluation method of quality assurance involves asking each participant to complete a brief checklist that queries the content of the session (e.g., “Did the therapist discuss the relationship between guilt and trauma?”). This method provides estimates of inter-rater reliability. We will maintain inter-rater reliability at $\boxed{?} = .90$. In addition, therapists will keep a session-by-session “TrIGR Session Tracking Form” and “SCT Session Tracking Form” which includes self-ratings about the “% of time” of each session was spent “using the manual” and covering the relevant module content.

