The Clinician-Administered PTSD Scale for DSM-5 [CAPS; 67] is a semi-structured interview used to assess PTSD diagnostic criteria and severity. Respondents select up to three of the most traumatic events they have experienced, and those events are used as the basis for assessing PTSD symptoms. The CAPS assesses each of the 20 items from the DSM-5 criteria B, C, D, and E and it has demonstrated high levels of internal consistency, good interrater reliability, and excellent convergent validity. The CAPS can be administered in about 60 minutes, and it has the advantages of categorical (diagnostic) or dimensional scoring of PTSD. The PTSD Checklist – 5 [PCL-5; 68] is a brief self-report instrument to measure PTSD symptom severity. It consists of 20 items, scored on a 5-point scale (0 = not at all to 5 = extremely), that correspond to the DSM-5 symptoms of PTSD. The PCL-5 is still being evaluated; however, preliminary studies report high internal consistency (alpha ranges between .95 and .97) and high correlations with the original PCL (between .88 and .97) [69].

Depression. The Patient Health Questionnaire [PHQ-9; 70] is a self-report scale listing common symptoms of depression. It is among the most widely used self-report depression measure in clinical populations, facilitating comparison between this investigation and others.

Exploratory outcomes. The Timeline Follow-back [TLFB; 71] will be employed at all assessment points to evaluate alcohol and other substance use during the 90 days preceding each interview. The Quantity-Frequency Index[72] and maximal consumption will be calculated for alcohol use. Drug use indices will be similarly derived for opiates, marijuana, and other drugs. The TLFB will be used at each follow-up to establish: percentage days heavy drinking, percent days abstinent, length of initial

abstinence, length of use episodes, severity of relapse and current alcohol/drug use pattern. A self-report Substance Use Inventory [SUI; 73] will be administered bi-weekly at treatment sessions. The inventory asked patients on which of the preceding seven days they had used alcohol or any of seven major types of drugs. Participants will be administered the AUD and SUD sections of the SCID for DSM-5 at baseline.

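### The 90-day Timeline Follow-back at the immediate post-treatment visit includes pre-treatment days, so percent-days effects on substance use are understated at that visit only

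*Combined protocol and SAP*

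**What the plan says.** Section 9.8.1 (Exploratory outcomes) applies the TLFB at every assessment and has it cover alcohol and drug use "during the 90 days preceding each interview". From it the plan derives, at each follow-up, percent days of heavy drinking, percent days abstinent, length of initial abstinence, length of use episodes, severity of relapse and current use pattern. It also derives a quantity-frequency index and maximal consumption for alcohol.

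Under section 9.1, participants "receive 6 sessions of TrIGR or SCT in individual format" and then "complete a follow-up assessment immediately post-treatment, and 3- and 6-months later". The interval between sessions is not stated. Three places bear on it:

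- Section 9.7.4 refers to "treatment manuals with weekly objectives, outcomes, and agendas".
- Section 9.3 says "Participants will also complete brief weekly self-report assessments (15 minutes) during treatment".
- Section 9.2 says "Participant recruitment and enrollment will occur in months 6 to 34, with the intervention period occurring from months 6 to 36".

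The exploratory analyses in section 9.11.2 ask whether TrIGR gives "greater reductions in alcohol/substance use, will be explored using mixed effect method", as for Hypothesis 1. That model takes responses from baseline to 6 months, so the post-treatment TLFB value enters as a post-baseline response. No readable text shortens the look-back at that visit, limits scoring to days since baseline or session 1, or leaves the visit out.

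**The concern.** A look-back longer than the treatment period reaches past session 1. Days on which neither therapy could have acted are then averaged into the value labelled post-treatment. This has three consequences.

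1. The between-arm difference on averaged indices is pulled toward zero at this visit. A larger sample does not cure that.
2. The 3- and 6-month windows are clear of pre-treatment days, so a steady benefit would seem to grow after treatment ends. The secondary aims ask whether gains are maintained, and section 9.11.2 chooses the form of the time model from plots of the outcome. The artefact could therefore affect both the model and its interpretation.
3. Indices that are not averages can be set by pre-treatment days. One heavy day before session 1 can fix the maximal consumption, and initial abstinence may be counted from a date before treatment.

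**Working it through.** The plan gives no effect size, power or window-share figure for substance use, so there is none to reproduce. One timeline check agrees: months 6 to 34 give 34 − 6 = 28 months of enrolment, as in section 9.5.3.

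**Inputs.**
- W = 90 days (section 9.8.1).
- D = days from session 1 to the post-treatment interview. Six weekly sessions give about 42 days (inferred from sections 9.3 and 9.7.4). The gap between the end of enrolment and the end of the intervention period, 36 − 34 = 2 months, gives about 61 days (section 9.2).
- g = days from baseline to session 1. It is not stated; 14 days is assumed for illustration.

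**Shares.** Pre-treatment share = max(0, W − D)/W. Pre-baseline share = max(0, W − D − g)/W. For an effect constant from session 1, the part retained by a window average is 1 minus the pre-treatment share.

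| D (days) | Pre-treatment share | Effect retained | Pre-baseline share, g = 14 |
|---|---|---|---|
| 42 | 48/90 = 53% | 0.47 | 34/90 = 38% |
| 49 | 41/90 = 46% | 0.54 | 27/90 = 30% |
| 56 | 34/90 = 38% | 0.62 | 20/90 = 22% |
| 61 | 29/90 = 32% | 0.68 | 15/90 = 17% |

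Outside this range, D = 35 (five weekly intervals, interview on the day of session 6) gives 55/90 = 61%, and D = 84 gives 6/90 = 7%. The share is zero only when D is at least 90.

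**Later visits.** Three months is about 91 days, so that 90-day window starts after the post-treatment visit. The 6-month window is also clear. A constant effect E therefore appears as about 0.47E to 0.68E, then E, then E.

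**Effect on precision.** With g = 0, the days common to both windows cancel in the change from baseline:

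change = (D/90) × (mean of treatment days − mean of the first D baseline days).

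The raw effect and much of its standard deviation (SD) shrink together. Let s_c be the SD of true person-level change and s_e the SD of independent day-to-day variation. The standardised effect per unit of true effect is:

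- 90-day window: (D/90) / √[(D/90)²s_c² + 2D s_e²/90²]
- days since session 1 only: 1 / √[s_c² + s_e²(1/D + 1/90)]

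With D = 42, s_c = 0.1 and s_e = 1, these are 4.17 and 4.72, a loss of 1 − 4.17/4.72 = 12%. With D = 61, s_c = 0.3 and s_e = 0.5, they are 3.19 and 3.21, a loss of about 1%. A second assumed model, with a stable person level, autocorrelated daily use (correlation 0.90 to 0.98 between adjacent days) and g of 0 or 14, gives losses of about 10-32%. All these variances are assumptions.

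**The case against.** **Treatment length is inferred.** Section 9.2 is a project timeline, not a limit for each participant, and missed weeks would lower the pre-treatment share. Table 3 could not be read in the available copy and might state a different window. This stands: the 32-53% is conditional on 6 weeks to 2 months of treatment.

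**The outcome is exploratory and partly covered elsewhere.** The Substance Use Inventory, given every two weeks with a seven-day recall, samples use during treatment. The TLFB's current use pattern need not be a 90-day average. Neither replaces the percent-days indices that the plan requires at every follow-up, so this limits the importance of the point without removing it.

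**A reader might infer a collapse in power.** Applying the dilution (42/90 and 60/90) to a 0.5 SD difference with 60 per arm (75 less 20% attrition), in a t-test of post-treatment values with unchanged SD, takes power from about 77% to 25-44%. The documents do not support this. The planned mixed model uses baseline, and the overlap also shrinks the SD of change. The 0.5 SD effect and the power statements in section 9.11.2 concern Hypotheses 1-3, not substance use.

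**A reader might also infer that the whole third to half of the window is double-counted with baseline.** That holds only if session 1 falls on the day of baseline. Randomisation comes between the two, and the gap is not stated.

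**Conclusion.** The point holds as a bias in the estimate at one visit. If treatment takes 6 weeks to 2 months, the stated rule fills 32-53% of the post-treatment window with pre-treatment days. It reports a constant effect on percent-days indices at about 47-68% of its size, followed by an artificial rise at 3 months. The double-counted part is smaller by the gap from baseline to session 1.

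The loss of standardised effect in a baseline-adjusted analysis is modest by comparison, from about 1% to 32% depending on assumed variances, and no power claim should rest on it. Only an exploratory outcome is affected, at one of three post-baseline visits. The change is still worth making before analysis, because alcohol and substance use is named in exploratory Objective 1, mild to moderate use disorders are deliberately admitted, and the correction costs little.

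**What to change.** Keep the TLFB interview as it is and add a scoring rule to sections 9.8.1 and 9.11.2:

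1. **Percent-days and quantity-frequency indices.** At post-treatment, compute them only from days since session 1, or since baseline or randomisation, with the same rule in both arms. Keep 90 days at baseline, 3 months and 6 months.
2. **Indices that depend on window length** (maximal consumption, length of initial abstinence, length of use episodes). Exclude pre-treatment days at post-treatment. Then either use a window of equal length at the other visits or compare arms within visit only. Otherwise a 42- to 61-day maximum set beside a 90-day maximum would create a new artefact over time.
3. **Start date.** Choose it in advance. Session 1 removes all pre-treatment days but is undefined for anyone who never attends. Baseline or randomisation covers everyone but leaves the waiting days in: counting from baseline with an assumed 14-day gap, 14/(42 + 14) = 25% or 14/(61 + 14) = 19% of the window.

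The percent-days indices imply that use is recorded by day, so no new data are needed. The cost is a somewhat noisier post-treatment index, based on fewer days and on a number of days that differs between participants.

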In the second stage, we will perform sensitivity analyses for the impact that potentially informative missing data may have on the analyses. The selected method of data analysis is robust with respect to drop-out and missing data, unless the drop-out mechanism or cause of missing is informative. We will use pattern-mixture models to assess if there is bias due to drop out or missing data. These mixed models allow us to assess whether important estimates are dependent on missing data patterns, and provide overall estimates of effects by averaging over the various missing-data patterns [80]. In addition, we will consider the extension of the Pattern-Mixture models [81], which includes the incorporation of random effects in the Pattern mixture model, which allow subject-to-subject heterogeneity. All hypothesis tests will be intent-to-treat, using SPSS version 21, and will be two-sided at the .05 level where applicable. We will adjust p-values for multiple testing within each hypothesis separately by using a Bonferroni correction whenever more than one variable is being tested.

Type I error will be controlled through the following steps. The data analysis method we selected reduces the number of dependent variables drastically. We have restricted potential predictors to those with strong evidence and/or strong rationale for having an effect on the dependent variable, and in most cases we have further restricted potential predictors to one representative of each. Also, an adjusted significance level (.01 rather than .05) will be used if applicable.

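### Bonferroni within each hypothesis is valid, but Holm's step-down keeps the same .05 bound and misses fewer real H2 effects: a cheap improvement

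*Combined protocol and SAP*

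**What the plan says.** Section 9.11.1 sets the general rule. Tests "will be two-sided at the .05 level where applicable", and for multiplicity: "We will adjust p-values for multiple testing within each hypothesis separately by using a Bonferroni correction whenever more than one variable is being tested". No step-down, gatekeeping or other sequential procedure is named anywhere. The same section adds that "an adjusted significance level (.01 rather than .05) will be used if applicable", without saying when it applies.

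The rule affects two hypotheses:

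- **H2.** In section 9.11.2 the claim covers three measures: "significantly greater reduction in distress (BSI-18), shame (ISS), and significantly more improved in their quality of life (WHO-QOL-BREF"). In section 8 the same hypothesis covers five constructs: "significantly greater reductions in distress, shame, guilt cognitions, avoidant coping, and significantly more improvement in their quality of life". Both versions refer to the end of treatment and to follow-up.
- **H3.** Section 9.11.2 names three mediators: "guilt cognitions (TRGI Cognitions Scale), distress (BSI-18) and avoidant coping (COPE) will partially mediate the treatment effect on guilt severity (TRGI").

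The power paragraph in section 9.11.2 claims a "minimum of 90% power to detect the medium effect size for hypothesis 1 and 80% for hypothesis 2". It does not state the significance level behind either figure.

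**The concern.** Single-step Bonferroni compares every p-value in a family of m with .05/m. Holm uses that threshold only for the smallest p-value and relaxes it after each rejection. It needs the same p-values and no further assumption about how the outcomes are related. The sponsor expects TrIGR to improve several correlated outcomes, and this is the situation in which the relaxed thresholds matter. If the hypothesis is right, some real secondary effects would be reported as not significant under Bonferroni that Holm would have declared at the same .05 bound.

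**Working it through.** **1. Inputs.** From the documents: two-sided .05; Bonferroni within each hypothesis; m = 3 (section 9.11.2) or m = 5 (section 8) for H2; 150 participants allocated equally, so 75 per arm; a 0.5 SD difference at the last time point; 10% to 20% attrition; repeated-measures correlations of 0.2, 0.5 and 0.8. Assumed, because the documents do not give them: correlations of 0.3 to 0.6 between H2 measures, and equal effects on every measure whose effect is real.

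**2. The plan's own power figures.** One plausible configuration comes within 1 point of them: a group-by-time slope test, 75 per arm, four equally spaced assessments, dropout reaching 20%, compound symmetry with correlation 0.2, and no group difference at baseline.

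- H1 at .05: 89.4% (stated 90%). The implied noncentrality is 1.960 + 1.248 = 3.208.
- H2 at .05/3 (critical value 2.394): Φ(3.208 − 2.394) = Φ(0.814) = 79.2% (stated 80%).
- H2 at .05/5 (critical value 2.576): Φ(3.208 − 2.576) = Φ(0.632) = 73.6%.

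The stated 80% for H2 is therefore consistent with plain Bonferroni over three tests. Other configurations do not match. For example, assumed visit times of 0, 1.5, 4.5 and 7.5 months give 87.2% and 75.9%.

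**3. The two procedures with m = 3.** Bonferroni compares all three p-values with .05/3 = .0167. Holm orders them, compares them in turn with .05/3 = .0167, .05/2 = .025 and .05/1 = .05, and stops at the first failure. Invented example: p = .010, .020, .040. Bonferroni-adjusted values are .030, .060 and .120 (one rejection). Holm-adjusted values are .030, .040 and .040 (three rejections).

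**4. Error control.** With m₀ true null hypotheses, Holm can make a false rejection only if the smallest of their p-values is at or below .05/m₀. That probability is at most m₀ × .05/m₀ = .05, whatever the dependence.

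**5. Size of the gain, m = 3.** Each real effect has 80% power at .05/3, so the noncentrality is 2.394 + 0.842 = 3.236. Correlated normal test statistics were simulated at correlations 0.3 and 0.6 (400,000 sets per scenario).

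| Real effects | Power per real effect, Bonferroni | Holm | Actual familywise error, Bonferroni → Holm |
|---|---|---|---|
| one of three | 80% | 80% | about 3% → about 4% |
| two of three | 80% | about 83% | about 1.6% → about 4% |
| three of three | 80% | 86–87% | no false rejection possible |

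Bonferroni never rejected a hypothesis that Holm retained. With all three real, the chance of at least one finding is identical under both methods (about 97% at correlation 0.3, about 94% at 0.6), because the first threshold is the same.

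**6. If the family is five.** With 80% per measure at .05/5 and the same correlations, Holm gives 80% with one real effect, 81–82% with two, 83–84% with three and 88–89% with all five. If the design in step 2 is spread over five measures instead, the starting point is 74% under Bonferroni, and Holm gives 82–85% when all five are real (correlations 0.7 to 0).

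**7. H3.** A simulated Sobel test was run with 120 participants (150 less 20%), both paths at 0.39 and all three mediators real. It gives 80% against 90–91% if the treatment variable is treated as continuous, and 20% against 25% if it is coded 0/1 as in a two-arm trial. Mediator residual correlations of 0.3 to 0.5 were assumed. The simulation covers the Sobel test alone, not the other conditions that section 9.11.2 requires for mediation.

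**The case against.** The strongest reply is that nothing is broken. Bonferroni is pre-specified, valid and simple, it gives matching simultaneous confidence intervals, and the stated 80% for H2 can be reproduced under it with three tests. All of that stands. It is also fair that the gain depends on how many effects are real: about 3 points with two of three, and practically none with one. Holm also spends more of the error allowance. The two methods share a bound, not an actual error rate.

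A reader might infer from the wording of H2 that all outcomes must be significant together. The gain would then look much larger: the chance of showing all three goes from 57–64% to 74–78% in the setting of step 5. The documents do not support that reading. They never define H2 success as every outcome significant, and adjusting per variable implies separate claims. If an all-or-nothing claim were intended, testing each outcome at .05 would need no multiplicity correction (all-three power about 75.5% to 79%), so neither method would be the indicated one.

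A reader might also infer that Bonferroni discards power for nothing, or that Holm secures H3. The first ignores the simpler intervals and the lower actual error. The second fails because the H3 result ranges from a gain of about 10 points to one of about 5 points on a very low base, depending on an assumption the plan does not state.

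Finally, substituting one word would not be enough. Holm needs a fixed family as much as Bonferroni does, and the plan does not fix one. This objection is right, and the fix takes it in.

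**Conclusion.** The point holds as a cheap improvement in efficiency, not as the correction of an error. For three H2 measures the gain per measure is 6 to 7 points if all three effects are real, about 3 if two are, and none of note if one is. The chance of at least one finding does not change when all are real. These sizes rest on the assumed equal effects, correlations of 0.3 to 0.6 and 80% power at .05/3. That Holm never rejects less, and that it keeps the .05 bound, depends on none of these assumptions.

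For H3 the same ordering applies to the three mediator tests, but the size of the gain is not established.

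The unsettled family matters under either method. With three measures in one place and five constructs in another, the adjusted p-values cannot be computed unambiguously. The .01 rule leaves the decision threshold open as well. It happens to equal .05/5, but the plan does not link it to the five-construct list.

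**What to change.** In section 9.11.1, replace the Bonferroni correction with *Holm step-down adjusted p-values within each hypothesis that tests more than one variable (H2, and the three mediator tests of H3), at a two-sided familywise level of .05*. In the same edit:

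- List the H2 family once and use that list in sections 8 and 9.11.2. State which time points count as separate tests and which WHO-QOL-BREF score is tested, since section 9.8.1 gives it four domains.
- Delete the .01 rule, or say exactly which tests it governs and how it combines with the adjustment.

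The cost is a few sentences, with no change to participants, visits or data. Simultaneous intervals become less simple; unadjusted 95% intervals, labelled as such, can be shown beside the Holm-adjusted p-values. Actual familywise error will be higher than under Bonferroni but within .05. The change should be made before H2 or H3 outcomes are compared by arm, noting that section 9.2 allows preliminary analyses from the second year. If they have already been compared, Bonferroni should remain the confirmatory method and Holm results should be labelled post hoc.
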